1.1 Data Management and Data Quality

The first randomization involves allocation to CPS vs. SMS using a 1:1 allocation ratio. This step will use stratified randomization in permuted blocks to achieve balance in distribution of behaviorally and perinatally infected youth. The REC data team will program the randomizer in Qualtrics and will not participate either in the intervention delivery or in the adherence reinforcement steps. The protocol team will monitor race, ethnicity, and gender to ensure balanced distribution at the first stage. After 6 months, stratified randomization will occur with permuted blocks within each trajectory. Since second stage randomization is dependent on first stage response status, we will only maintain the balance within each first stage treatment outcome when randomizing at the second stage.

Following the Analytic Core's (AC) standard quality assurance, including checking for outliers and abnormal values using graphical methods, we will verify that the distributions of measures meet the assumptions of the statistical tests to be used, applying a formal test such as the Shapiro-Wilk's test [60]. Transformations will be used when distributional assumptions are not fulfilled. Tests will be conducted to identify potential relationships among baseline demographic and clinical variables and our dependent variables and to see whether they are balanced between groups. If a baseline variable is not balanced between groups and is correlated with the dependent variable ($r > .30$), we will include this variable as a covariate in subsequent analyses. Since we will test more than one primary hypothesis with one primary outcome variable (VL suppression), the Hochberg step-up multiplicity adjustment will be used with a two-tailed family wise alpha-level of .05 [61]. All other tests described below will each have a two-tailed alpha-level of 0.05. Outcome analyses will be based on the principle of intention-to-treat [62].

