1.2 Quantitative Analysis Plan

Original Primary Hypotheses: 1. Youth randomized to CPS will have significantly greater VL suppression (primary outcome) and self-reported medication adherence (secondary outcome) at 24 weeks than those in SMS group. 2. Non-responders randomized to CPS with incentives will have significantly greater VL suppression (primary outcome) and self-reported adherence (secondary outcome) than those randomized to SMS with incentives.

Original Secondary Aims: a) Conduct an exploratory evaluation of tapering the intensity of CPS and SMS (among responders) vs termination after completion of the 24 week intervention to determine if this improves the durability of intervention effects; b) Explore the relative efficacy of the individual intervention sequences embedded within the SMART design for responders and non-responders; and c) Describe moderators of the treatment effect, including demographics, mode of infection, substance use, and mental health. [NOT COMPLETED DUE LOW RENTENTION]

Updated Primary Outcome: Originally, we plan to treat VL suppression as our primary outcome for both co-primary hypothesis. Primary end-point for H1 was at 24 weeks when the proximal outcome was used to determine responder status, while for H2 the Distal outcome was at end of 12 months (or 72 weeks). Due to the difficulty in collecting viral load we proposed to change the primary outcome to a combination of VL suppression and self-reported adherence (SRA). Primary end-points for both co-primary hypothesis is now at 48 week.

Rationale of new definition of Primary Outcome: Since the VLS data may not be available for a significant number of subjects, we plan to use SRA as an additional primary outcome. The usefulness and appropriateness of the usage of these two depends upon the concordance of two measures. To determine that for those subjects we have both VLS and SRA data available, we will first construct a 2×2 contingency table and conduct a chi-square test of association. If they agree on 80% or more cases we will proceed to define (and analyze) the primary outcome as following:

- 1) For any data collection point and randomization event, if VLS data is available it will be used as primary outcome. When VLS data is not available, SRA will be used as primary outcome. This composite definition will be used as primary outcome and will have sufficient power based on hypothesized effect size.

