- 2) In case it fails to agree at least 80% cases, we will analyze VLS and SRA as two separate primary outcomes. Two measures cannot be combined, as they do not match sufficiently. In this situation, it is likely that VLS as primary outcome will not have sufficient sample size to produce an appropriately powered analysis, albeit, SRA may still produce a powered analysis provided SRA is available for all subjects. Note though no conclusion about VLS can be drawn from the outcome of SRA analysis.

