1.2.1 Primary Analysis Plan

The primary analysis will be a comparison of SRA (primary outcome) between the CPS and the SMS group at the end of first stage of randomization. This will be performed using a χ^2 test. We will also compare the VL suppression between the two groups for those available subjects, albeit this is no longer treated as primary outcome. Since SRA (and VL) is a continuous measure, we will use two-sample t-test to conduct this analysis. We will also compare the self-reported medication adherence rate (secondary outcome) between the two groups using a χ^2 test. All the primary analyses will be based on initial assignment to groups, using the ITT principle. Each of the primary hypotheses will be tested using linear mixed-effects (LME) regression analyses.¹⁰⁴ For testing primary hypothesis 1 (PH1), the model will include up to 3 repeated assessments of VL suppression (weeks 0/baseline, 12, 24, 36, 48). For primary hypothesis 2 (PH2), we will only focus on non-responders (for both CPS and SMS at stage 1) and compare the SRA as dependent variable using a repeated measure LME (weeks 0/baseline, 12, 24, 36, 48). In an effort to get the outcome for PH2 some subject may have final outcome at latter date than 48 weeks. Each LME model will include a random intercept and slope and fixed effects for adherence intervention group, and time, as well as the stratification variables: clinical site, age, gender. A likelihood ratio test will examine the incremental contribution of the group by time interaction, which represents the interaction of interest for PH1 and PH2, testing for a differential adherence intervention effect over time. The decision rule for each primary hypothesis calls for rejection of H_0 if this interaction is statistically significant using the Hochberg adjustment. A site by group interaction will be also examined and included in each model (above) if significant at the 0.05 level. The purpose of the LME based analysis for the primary aim is to determine which of the first-stage intervention, CPS or SMS, is associated with the most improvement in VL and adherence, regardless of which second-stage treatment participants received. Due to contraction of sample size compared to our original plan, we do not plan to adjust α for multiple of testing. In addition to PH1, for those subjects we have VL suppression data available we would perform similar LME to test for its significance. We also expect some subjects with complete VL data and many with partial VL data for

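### If VLS and SRA agree in under 80% of cases, the SAP makes both primary but defines no error-controlled family for the four resulting tests, and its sections conflict on adjustment and on whether VLS is primary

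*SAP*

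**What the plan says.** SAP 1.2 first checks how often VLS and SRA agree in participants who have both. At 80% agreement or more there is one primary outcome: VLS where available, otherwise SRA. Of this the SAP says "This composite definition will be used as primary outcome and will have sufficient power based on hypothesized effect size". Below 80%, item 2 applies: "In case it fails to agree at least 80% cases, we will analyze VLS and SRA as two separate primary outcomes". Item 2 expects VLS to be short of data in that case and adds: "Note though no conclusion about VLS can be drawn from the outcome of SRA analysis".

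Two primary hypotheses run through both branches. PH1 compares CPS with SMS; PH2 compares CPS with incentives against SMS with incentives among non-responders. The SAP sets one time point for the pair: "Primary end-points for both co-primary hypothesis is now at 48 week".

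On multiplicity, SAP 1.1 says: "Since we will test more than one primary hypothesis with one primary outcome variable (VL suppression), the Hochberg step-up multiplicity adjustment will be used", at a "two-tailed family wise alpha-level of .05". It then adds: "All other tests described below will each have a two-tailed alpha-level of 0.05". SAP 1.2.1 rejects each primary null hypothesis "if this interaction is statistically significant using the Hochberg adjustment". Later in the same paragraph it says that, because the sample has shrunk, alpha will not be corrected for multiple testing. SAP 1.2.1 also names SRA as the primary outcome and says VL suppression has lost that status, yet the PH1 model it describes has VL suppression as its dependent variable.

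SAP 1.2.4 computes power at two-sided alpha 0.05. The protocol's Sample Size and Power text used 0.025, the first Hochberg step for two hypotheses.

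**The concern.** The primary outcome was revised, but the multiplicity sentence in SAP 1.1 still describes several hypotheses on one outcome, VL suppression. That is a two-test family. Item 2 of SAP 1.2 can double the number of primary tests, and nothing extends the family to cover them, ranks VLS against SRA, or says whether a hypothesis needs support on one outcome or on both.

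The branch is entered on the basis of observed data, namely the agreement rate. If the family is not fixed beforehand, an analyst could report a primary success on whichever outcome gave it, while citing a family-wise 0.05 that the procedure may not deliver. Poor agreement is also where the two outcomes are least likely to move together, so the less correlated end of the range below is the more plausible one.

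**Working it through.** **Inputs.** Two hypotheses and two outcomes in the fallback (SAP 1.2); family-wise alpha 0.05, two-sided (SAP 1.1); 60 per group, 10% attrition, standardized effect size (ES) 0.55, t-test at two-sided 0.05 (SAP 1.2.4). Assumed, because the documents do not give them: PH1 and PH2 test statistics are independent, and the VLS and SRA statistics within a hypothesis have correlation r, run from 0 to 0.8.

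**The plan's own figure.** n per arm = 2(1.960 + 0.842)² / 0.55² = 51.9, so 52 per arm and 104 in total; 104 / 0.90 = 115.6, so 116. This matches the SAP power-table row for ES 0.55 and p = 0.5. With 60 × 0.90 = 54 per arm, noncentral-t power is 0.808. The stated 80% is reproduced, at alpha 0.05 for a single test.

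**Number of tests.** Composite branch: 2 hypotheses × 1 outcome = 2. Fallback under item 2: 2 × 2 = 4. Fallback if SAP 1.2.1 governs and VLS is not primary: 2.

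**Family-wise error, closed form at r = 0.**
- Two tests, unadjusted: 1 − 0.95² = 0.0975.
- Two tests, Hochberg: (1 − 0.975²) + 0.025² = 0.0494 + 0.0006 = 0.050.
- Four tests, unadjusted: 1 − 0.95⁴ = 0.1855.
- Four tests, Hochberg run once per outcome: two families at 0.05 each, 1 − 0.95² = 0.0975.

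**Family-wise error over r** (four null tests, simulation with 2,000,000 draws):

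| r between VLS and SRA tests | 0 | 0.2 | 0.4 | 0.6 | 0.8 |
|---|---|---|---|---|---|
| No adjustment | 0.185 | 0.183 | 0.178 | 0.168 | 0.150 |
| Hochberg separately per outcome | 0.097 | 0.097 | 0.094 | 0.089 | 0.080 |
| One Hochberg family of four | 0.049 | 0.049 | 0.048 | 0.046 | 0.041 |

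**Power at the first step.** With four tests the strictest Hochberg step is 0.05 / 4 = 0.0125; with two it is 0.025. A test must meet that step when none of the others is significant.
- PH1, ES 0.55, 54 per arm: 0.81 at 0.05, 0.72 at 0.025, 0.62 at 0.0125.
- PH2, assuming 50% response and 10% attrition: 120 × 0.90 × 0.50 = 54 non-responders, 27 per arm. Power is 0.51 at 0.05, 0.39 at 0.025, 0.30 at 0.0125.
- Sample size for 80% power on a two-group comparison at 0.0125: 74 per arm, 148 in total, and 148 / 0.90 = 164.4, so 165 against the planned 120.

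These figures assume complete outcome data on the participants counted, so they are too high for VLS if data are missing as item 2 expects.

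**The case against.** A reader might infer that the fallback is uncontrolled on every reading, with four primary tests as a settled fact. The documents do not support that, for three reasons.

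First, SAP 1.2.1 says VL suppression is no longer primary and treats its analysis as an addition for participants with data. If that section governs, the fallback has two primary tests. This stands as a limit on the count. It does not dispose of the point: SAP 1.2.1 never mentions the 80% rule, its own PH1 model uses VL suppression, and item 2 is the only text that says what happens when agreement fails.

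Second, the Hochberg decision rule in SAP 1.2.1 does not repeat the one-outcome wording. Read as covering every primary p-value, it holds the error at or below 0.05. This also stands: the family is undefined and contradictory, not necessarily uncontrolled. Running Hochberg once per outcome is a natural reading of SAP 1.1, but no sentence prescribes it.

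Third, a reader might infer that significance on either outcome makes the trial positive. No such rule is written. If both outcomes had to be significant for a hypothesis, there would be no inflation from having two. Item 2's warning that SRA results say nothing about VLS restricts what may be claimed; it limits interpretation and does not set an error rate.

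It can also be said that the no-adjustment sentence is the larger problem, since taken alone it leaves the composite branch at 0.0975 too. That is correct, and the passages should be reconciled together. Settling that sentence in favour of Hochberg would still leave the fallback family undefined.

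**Conclusion.** The point holds as a conflict and a gap: in the under-80% branch the stated family-wise 0.05 is not secured, because SAP 1.1, SAP 1.2 item 2 and SAP 1.2.1 do not agree on which outcomes are primary or whether alpha is adjusted. The error rate depends on the reading:
- item 2 governs, Hochberg per outcome: about 8% to 9.8%;
- item 2 governs, no adjustment: about 15% to 18.5%;
- item 2 governs, one Hochberg family of four: at most 5%;
- SAP 1.2.1 governs and VLS is not primary: 5% with Hochberg, about 9.75% without.

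The first two ranges also assume that significance on either outcome counts. All the figures assume PH1 and PH2 independent; the four-test ranges also depend on the assumed VLS-SRA correlation of 0 to 0.8. The stronger claim, that this branch has no control whatever, goes beyond the text. The issue is confined to one branch for the outcome count, but the adjustment conflict reaches the composite branch as well.

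**What to change.** State in SAP 1.2, for each branch, which outcomes are primary. In item 2, define the fallback family before the agreement result is known, by one of two routes:
- *One family.* The four tests (PH1 and PH2, each on VLS and on SRA) form a single Hochberg family at two-sided 0.05.
- *Fixed order.* VLS and SRA are ranked in advance. PH1 and PH2 are tested by Hochberg on the first outcome, and the second outcome is tested only if both are rejected on the first.

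Under either route, limit each conclusion to the outcome on which it was reached. Change the single-outcome wording in SAP 1.1 to match. Amend both conflicting statements in SAP 1.2.1, the one removing VL suppression from primary status and the one declining to adjust alpha; editing SAP 1.1 and item 2 alone would leave the contradiction in place. If the team prefers no adjustment, it should drop the family-wise 0.05 claim and state the resulting error rate.

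The cost is SAP wording plus an honest power statement. Under four-test Hochberg the strictest step is 0.0125, where power at ES 0.55 is about 62% for PH1 (81% at 0.05) and about 30% for PH2 under the 27-per-arm assumption, and lower for VLS with missing data. A fixed order avoids the 0.0125 step, but the second outcome may never be tested, which matters if VLS is placed first and is short of data.

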1.2.1 Primary Analysis Plan

The primary analysis will be a comparison of SRA (primary outcome) between the CPS and the SMS group at the end of first stage of randomization. This will be performed using a χ^2 test. We will also compare the VL suppression between the two groups for those available subjects, albeit this is no longer treated as primary outcome. Since SRA (and VL) is a continuous measure, we will use two-sample t-test to conduct this analysis. We will also compare the self-reported medication adherence rate (secondary outcome) between the two groups using a χ^2 test. All the primary analyses will be based on initial assignment to groups, using the ITT principle. Each of the primary hypotheses will be tested using linear mixed-effects (LME) regression analyses.¹⁰⁴ For testing primary hypothesis 1 (PH1), the model will include up to 3 repeated assessments of VL suppression (weeks 0/baseline, 12, 24, 36, 48). For primary hypothesis 2 (PH2), we will only focus on non-responders (for both CPS and SMS at stage 1) and compare the SRA as dependent variable using a repeated measure LME (weeks 0/baseline, 12, 24, 36, 48). In an effort to get the outcome for PH2 some subject may have final outcome at latter date than 48 weeks. Each LME model will include a random intercept and slope and fixed effects for adherence intervention group, and time, as well as the stratification variables: clinical site, age, gender. A likelihood ratio test will examine the incremental contribution of the group by time interaction, which represents the interaction of interest for PH1 and PH2, testing for a differential adherence intervention effect over time. The decision rule for each primary hypothesis calls for rejection of H_0 if this interaction is statistically significant using the Hochberg adjustment. A site by group interaction will be also examined and included in each model (above) if significant at the 0.05 level. The purpose of the LME based analysis for the primary aim is to determine which of the first-stage intervention, CPS or SMS, is associated with the most improvement in VL and adherence, regardless of which second-stage treatment participants received. Due to contraction of sample size compared to our original plan, we do not plan to adjust α for multiple of testing. In addition to PH1, for those subjects we have VL suppression data available we would perform similar LME to test for its significance. We also expect some subjects with complete VL data and many with partial VL data for

PH2. An exploratory analysis is also planned where we define a composite binary outcome as 1 if either SRA or VL suppression ($VL < 200$ copies/ML) is achieved and 0 otherwise. This binary composite outcome variable will be analyzed using mixed effect GLM. Since our modified design guarantees availability of at least one of the two defining quantities this exploratory analysis ensures usage of full data.

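### The SAP gives conflicting primary outcomes, primary visits and alpha rules for its two primary hypotheses, and the protocol still carries another outcome, schedule and sample size

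*SAP*

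**What the plan says.** **Outcome and visit, SAP 1.2.** Under the heading for the updated primary outcome, the SAP cross-tabulates VLS against SRA. "If they agree on 80% or more cases we will proceed to define (and analyze) the primary outcome as following", VLS is used where it exists and "When VLS data is not available, SRA will be used as primary outcome". Otherwise, "In case it fails to agree at least 80% cases, we will analyze VLS and SRA as two separate primary outcomes". On timing: "Primary end-points for both co-primary hypothesis is now at 48 week".

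**Outcome and visit, SAP 1.2.1.** "The primary analysis will be a comparison of SRA (primary outcome) between the CPS and the SMS group at the end of first stage". VL suppression is compared as well, "albeit this is no longer treated as primary outcome". The same section labels the self-reported adherence rate secondary. For primary hypothesis 1 (PH1), "the model will include up to 3 repeated assessments of VL suppression (weeks 0/baseline, 12, 24, 36, 48" and so on, which is five time points. The model for primary hypothesis 2 (PH2) is on SRA.

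**Test, SAP 1.2.1.** SRA is compared by chi-square, then described as continuous and given a t-test. The only decision rule is a likelihood ratio test of the group-by-time interaction in a linear mixed model.

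**Alpha.** SAP 1.1 and the decision rule in 1.2.1 use Hochberg, at a two-sided family-wise 0.05 in SAP 1.1. Later in 1.2.1, citing the smaller sample, the SAP says alpha will not be adjusted. SAP 1.2.4 powers at 0.05.

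**Protocol 16.0.** VL suppression is the single primary outcome, modelled at months 0, 3, 6 and 12 with Hochberg. Power is set at alpha 0.025 with 190 participants, although Protocol 11.0 enrols 120.

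**The concern.** Primary variable, visit, decision test and error rate together define a confirmatory result. All four should be fixed in one place, and here none is. The conflict does not come from superseded text: SAP 1.2 marks the old hypotheses as original, while its update, SAP 1.1 and SAP 1.2.1 are all in force.

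If one hypothesis gives p = 0.03 and the other exceeds 0.05, the first is significant under the no-adjustment sentence and not under Hochberg. A reader of the final report could not tell which analysis was the planned one.

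The step that selects the primary outcome also cannot be run as written. A 2×2 agreement table needs a cut-off for SRA success, and none is given as an outcome definition. Protocol 9.0 uses SRA of 80% or less over 4 weeks, but only for eligibility.

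**Working it through.** **1. The current passages side by side**

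| Item | SAP 1.2 | SAP 1.2.1 | Protocol 16.0 |
|---|---|---|---|
| Primary variable | VLS, else SRA; or two primaries | SRA named; PH1 model on VL suppression, PH2 model on SRA | VL suppression |
| Visit | Week 48 | End of first stage; mixed models to week 48 | First stage; model at months 0, 3, 6, 12 |
| Treatment-effect test | None named | Chi-square, t-test, and group-by-time test carrying the decision | Chi-square, and group-by-time test carrying the decision |
| Alpha | Not stated | Hochberg, then no adjustment | Hochberg |

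No reading of 1.2.1 analyses the variable defined in 1.2. The end of the first stage is itself unsettled: Protocol 5.0 re-randomises at 3 months, while Protocol 16.0 and SAP 1.1 say 6 months.

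**2. The plan's own power figure**

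Inputs from SAP 1.2.4: 60 per group, 10% attrition, effect size 0.55, two-sided t-test, alpha 0.05. Evaluable per group: 60 × 0.9 = 54. Noncentrality: 0.55 × √(54/2) = 2.858, with 106 degrees of freedom.

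- Alpha 0.05: critical t = 1.983, power 80.8%. The stated 80% is reproduced.
- Alpha 0.025: critical t = 2.274, power 72.0%.

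Under Hochberg, PH1 is tested at 0.05 if the larger p-value is at or below 0.05 and otherwise at 0.025, so its power lies between these two figures.

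**3. Family-wise error**

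- Two independent tests at 0.05: 1 − 0.95² = 9.75%. By simulation (2,000,000 draws) it is 9.1% if the tests correlate 0.5. Hochberg with independent tests: 5.0%.
- Fallback with two outcomes for each of two hypotheses, assuming the hypotheses independent and the outcomes correlated 0.3, 0.5 or 0.7 within each: 18.1%, 17.3% and 16.0% unadjusted; 4.8 to 4.9%, 4.7% and 4.4% with Hochberg over four tests.

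**4. How far the two outcomes could differ**

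At exactly 80% agreement, VLS and SRA score 20% of youths with both measures differently. If all 108 evaluable youths (120 × 0.9) had a VL and that rate held at the visit, this is 0.20 × 108 = 21.6, about 22. Only those with a VL can differ between the SAP 1.2 composite and SRA.

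**5. Power for PH2**

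Per arm: 108 × (1 − p)/2, where p is the responder rate. At p = 0.5 (Protocol 16.0), this is 27. T-test, effect size 0.55:

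| p | n per arm | Power at 0.05 | Power at 0.025 |
|---|---|---|---|
| 0.4 | 32 | 58.2% | 46.6% |
| 0.5 | 27 | 50.9% | 39.4% |
| 0.6 | 22 | 43.0% | 31.9% |
| 0.7 | 16 | 32.5% | 22.7% |

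**6. If the outcome is binary at a single visit**

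Assumption: the same 0.55 SD shift dichotomised, with SMS success of 30, 40 or 50% (CPS 51.0, 61.7 or 70.9%). By chi-square, PH1 power at 54 per group is about 60 to 62% at 0.05 and 49 to 50% at 0.025. PH2 power at 27 per arm is about 35% and 25%.

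**The case against.** Much of the intent can be guessed. The decision rule in 1.2.1 belongs to the mixed model running to week 48, and the section allows some PH2 outcomes later than that, which fits the week 48 endpoint. The first-stage chi-square sentence closely follows Protocol 16.0 and carries no decision rule. A later sentence plans a similar model on VL suppression in addition to PH1, which suggests that PH1 was meant to be on SRA. The no-adjustment sentence is specific, gives a reason and matches alpha in SAP 1.2.4. The SAP also acknowledges that the outcome and sample size changed from the original plan, and on alpha the protocol agrees with SAP 1.1.

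These points stand as evidence of likely intent, but they do not reconcile the text. The first-stage SRA comparison is still called the primary analysis, an SRA-only reading still contradicts SAP 1.2, and both alpha statements remain in force.

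Three limits are accepted:

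- The figure of 22 in 108 is conditional. With half the VLs missing (an assumption) it would be about 11, and it says nothing about the size of the treatment effect.
- PH2 is weakly powered under every version, so that is not a consequence of the contradiction.
- The note "NOT COMPLETED DUE LOW RENTENTION" follows the secondary aims and speaks of retention. It does not show that outcome results were known.

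**Conclusion.** The concern holds and must be fixed before any result can be called the planned primary one. The contradictions on variable, visit and alpha lie within the current SAP and rest on no calculation. The protocol adds a further version of outcome, model schedule and sample size.

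The practical size is a family-wise error of 9.75% instead of 5% (independent tests), or about 16 to 18% under the fallback (assumed correlations). The claimed 80% power for PH1 is met at 0.05 but not at Hochberg's 0.025 step, where it is 72.0%. These power figures treat the analysis as a single-visit t-test, as SAP 1.2.4 does. A repeated-measures model would need its own simulation.

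**What to change.** 1. Name one primary variable and one visit for PH1 and PH2, and use them throughout SAP 1.2.1. The SAP 1.2 rule at week 48 is the natural candidate because it is headed as the update, but SAP 1.2.1 and 1.2.2 point to SRA, so the sponsor must confirm. State the SRA success cut-off (the complement of the eligibility threshold is one candidate) and the visits used for the agreement check.
2. Name one decision test that fits that variable and visit. A mixed-effects generalised linear model with a week-48 contrast is one option. The group-by-time test is another, if its link to week 48 is stated. List the remaining analyses as secondary, sensitivity or exploratory.
3. Keep one alpha statement: either Hochberg over two tests (four under the fallback), or no adjustment and no claim of family-wise control.
4. Define the PH2 set as everyone actually re-randomised to CPS or SMS with incentives.
5. Align Protocol 16.0 with the SAP. Reconcile the 3-month and 6-month re-randomisation statements (Protocol 4.0 and 5.0 against Protocol 16.0 and SAP 1.1). Reconcile also the handling of a missing month-3 VL: Protocol 5.0 counts it as non-response, SAP 1.2 falls back on SRA, and SAP 1.2.2 defines response by SRA. Which rule is right is for the sponsor.
6. Restate power for PH1 and PH2 separately under the chosen variable, test and alpha.
7. If any outcome data had been seen when the choice was made, say when and on what basis, and label it post hoc.

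**Cost.** Text changes only, in SAP 1.1, 1.2 to 1.2.2 and 1.2.4 and in Protocol 5.0 and 16.0; no new participants or data. The price is candour: PH1 power may have to be stated below 80%, PH2 power is about 51% or less at 27 per arm, and the choice may need to be declared post hoc.
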